#### 8.3.3 Analysis for confirmed PFS

For confirmed PFS, the Cox proportional hazards model will be used.

#### 8.3.4 Exploratory analyses

The following alternative approaches to the statistical analysis of OS, PFS and cPFS will be conducted as exploratory analyses.

#### 1. OS, PFS and cPFS: Cox model (ITT)

A Cox proportional hazards regression model [29] based on the ITT population will be used. The following baseline covariates will be assessed (one at a time) for their additional contribution to the statistical model, and each covariate showing a significant (P < 0.05) contribution will be included in the final model, for each endpoint separately. Subjects with missing data in the continuous variables (age, KPS) will be excluded from the respective analysis. Hazard ratios, estimates of survival to 6, 12, 18, 24, 30, 36, 42, 48, 54 and 60 months and 95% confidence intervals will be provided.

- Sex: Male / female
- Age at randomization: years
- MGMT status at randomization: Yes, No, unknown
- Karnofsky Performance Status at randomization: score
- Extent of resection: Complete, partial (or incomplete), unknown
- Absolute lymphocyte count at randomization: ≤ 1,000 /μL, > 1,000/μL, unknown

#### 2. OS, PFS and cPFS: Segmented (piecewise) Cox model (ITT)

The categorical, time-dependent, covariate PH model [29] tests whether the effect (coefficient) of a covariate changes with time (i.e. non-constant hazard ratio) over time segments of the study. This method has appeal because it not only detects non-proportionality, but allows it to be modelled validly. If the non-proportionality is linear, dichotomizing time could be sufficient. Alternatively, time could be categorized into four or five groups [30]. Within these groups, the assumption that the covariate effect is linear is more reasonable. There should be relatively equal numbers of events and censored observations across the time intervals to endure that the standard errors of the parameter estimates are relatively similar. Interactions are tested using the same likelihood test. The choice of time segments will be data driven; therefore, this analysis is not fully specified in this document.

#### 3. OS, PFS and cPFS: Cox model (PP)

The analyses described for the ITT population will be repeated in the PP population.

#### 4. OS, PFS and cPFS: Biomarker subgroups

The analyses described for the ITT population will be repeated in the ITT population excluding subjects with IDH-1 mutation and/or with chromosome 1p19q co-deletions.

#### 8.3.5 Further subgroup analyses for OS and PFS

The analyses described for the ITT population will all be repeated for each of the following subgroups (as in Table 5 above).

Table 8: Planned subgroup analyses

Ch	aracteristic	Subgroups		
•	Methylation status (MGMT):	Methylated, unmethylated		
•	Extent of resection:	
 
Complete, partial
 
		
		
 
Significant, minimal residual
 
		
•	Age categories:	
 
18-40, 41-50, 51-60, 61-64, ≥65
 
	1	
•	Sex:	
 
Male, female
 
		
•	KPS:	• 70 – 80, > 80 - 90, > 90 – 100		
•	Baseline lymphocyte count (/μL):	• ≤ median, > median		
		

≤ 1,000, > 1,000

		
		• ≤ 1,250, > 1,250		
•	RPA classification:	
 
Category III, category IV
 
		
•	Race:	
 
Caucasian, non-Caucasian
 
		
•	Residual tumor size at baseline:	
 
Based on quartiles
 
		
•	PD-L1 expression in tumor tissue:	
 
High, Low
 
		
•	PD-L1 status of circulating monocytes:	
 
> 80% positive cells, ≤ 80%
 
		
		• > 50% positive cells, ≤ 50%		
		• >10% positive cells, ≤ 10%		
•	Pre-existing CD8 T-cell density:	• ≤ median, > median		
•	Immunological responders to DCVax®-L:	• Yes, No		
•	Histology - GBM subtype:	
 
Proneural, Neural, Classical,
 
		
		Mesenchymal		
•	Immunoscore:	• 0 through 5		
•	Biomarker status:	
 
EGFR and PTEN genes, IDH1 WT
 
	Γ,	
		1p19q intact		
•	Rapid progressors (subjects with PFS ≤ 2m):	

Yes, No

		
•	Early progressors: (subjects with PFS ≤ 4m):	• Yes, No		

Job Number: 1555 Customer Reference: Study ID: 020221 SAP Version: 1.0

The hazard ratio for the treatments, and a 95% confidence interval for the HR, will be estimated for each subgroup.

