**Secondary Endpoint #3:** Progression-Free Survival (PFS) – Comparison between subjects randomized to DCVax®-L and those randomized to Placebo within Study 020221.

PFS as described in the original trial protocol uses modified Macdonald criteria to define disease progression and compares PFS between subjects randomized to DCVax®-L to those randomized to placebo within the Trial. The MacDonald criteria are no longer used in the field and cannot distinguish between actual disease progression and pseudoprogression. This endpoint will therefore likely be confounded due to pseudo-progression (PsPD) events being counted as PD. Such PsPD may be due to effects of surgery and/or radiation therapy or may also be induced by the DCVax®-L vaccine (i.e., T cell infiltration). This second form of PsPD occurs frequently in subjects receiving DCVax®-L, as may be seen through case studies.

**Secondary Endpoint #4:** Overall Survival (OS) – Comparison between subjects randomized to DCVax®-L and those randomized to Placebo within Study 020221.

OS as described in the original trial protocol compares survival in subjects randomized to DCVax®-L to those randomized to placebo within the Trial. Secondary Endpoint #4 is an OS analysis on this basis. However, due to the crossover option in the trial design for all patients in both arms of the Trial, and the fact that 90% of the total patients have received DCVax®-L, this means that the majority of subjects randomized to placebo have received DCVax®-L treatment following disease progression. This will result in a potential convergence of the survival curves if there is a survival benefit conferred on these crossover subjects as a result of the DCVax®-L treatment.

**Secondary Endpoint #5:** Tumor Response – Comparison between subjects randomized to DCVax®-L and those randomized to Placebo within Study 020221.

Resection of GBM typically focuses on removing the enhancing tissue as that is supposed to be the area of active tumor growth. Incomplete resections result in residual enhancing disease post-surgery and most patients also have non-enhancing disease areas surrounding the enhancing lesion. Tumor response will use pre- and post-randomization measurements of enhancing and non-enhancing disease. Modified RANO criteria will be applied per Cloughesy et al. [7], allowing for evaluation of non-measurable disease to determine response rates.

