#### 3.1.4 Progression-free survival

PFS is defined as the time from randomization until objective demonstration of tumor progression or death, whichever occurs first [10]. If neither tumor progression nor death are known to have occurred by the date of database lock, the date the subject was last known to be alive and progression-free will be used to calculate PFS, which will be considered censored.

When data points, especially in regards to radiographic imaging data, are missing, strong efforts will be made to obtain the missing study information. In spite of these efforts, there may be missing data regarding assignment of primary and secondary endpoints. Detailed rules for the definition of progression-free survival (modified Macdonald criteria) are provided in Appendix C.

Within-Study controls are used for this endpoint.

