#### 8.1.6 Subgroup analyses for OS and CS

The analyses described for OS and CS will all be repeated for each of the following subgroups, where the data allow.

Table 5: Planned subgroup analyses

Characteristic	Subgroups		
Methylation status (MGMT):	Methylated, unmethylated		
• Extent of resection:	
 
Complete, partial
 
		
	
 
Significant, minimal residual
 
		
Age categories:	• 18-40, 41-50, 51-60, 61-64, ≥65		
• Sex:	
 
Male, female
 
		
• KPS:	

70 – 80, > 80 - 90, > 90 – 100

		

 
Baseline lymphocyte count (/μL):
 
	• ≤ median, > median		
	

≤ 1,000, > 1,000

		
	• ≤ 1,250, > 1,250		

 
RPA classification:
 
	
 
Class III, Class IV
 
		
• Race:	
 
Caucasian, non-Caucasian
 
		

 
Residual tumor size:
 
	
 
Measurement; also quartiles
 
		

 
PD-L1 expression in tumor tissue:
 
	

High, Low

		

 
PD-L1 status of circulating monocytes:
 
	
 
> 80% positive cells, ≤ 80%
 
		
	
 
> 50% positive cells, ≤ 50%
 
		
	
 
>10% positive cells, ≤ 10%
 
		

 
Pre-existing CD8 T-cell density:
 
	• ≤ median, > median		

 
Immunological responders to DCVax®-L:
 
	• Yes, No		

 
Histology - GBM subtype:
 
	
 
Proneural, Neural, Classical,
 
		
	Mesenchymal		
• Immunoscore:	• 0 through 5		
Biomarker status:	
 
EGFR and PTEN genes, IDH1 WT,
 
		
	1p19q intact		

 
Rapid progressors (subjects with PFS ≤ 2m):
 
			
	• Yes, No		

 
Early progressors: (subjects with PFS ≤ 4m):
 
	• Yes, No		

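### SAP 8.3.5 (Table 8, and Table 5 where data allow) estimates treatment hazard ratios in subgroups defined by PFS and immune response after randomisation; these ratios are uninterpretable and may be biased in either direction

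*Combined protocol and SAP*

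**What the plan says.** SAP section 8.3.5 states that "The analyses described for the ITT population will all be repeated for each of the following subgroups", under a heading that names OS and PFS, and closes with "The hazard ratio for the treatments, and a 95% confidence interval for the HR, will be estimated for each subgroup". Most rows of Table 8 are baseline characteristics. Three are not: "Rapid progressors (subjects with PFS ≤ 2m", "Early progressors: (subjects with PFS ≤ 4m" and "Immunological responders to DCVax®-L", each split Yes/No.

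Table 5 in section 8.1.6 carries the same three rows for the comparison with external controls: "The analyses described for OS and CS will all be repeated for each of the following subgroups, where the data allow".

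On when these variables arise:
- Section 3.1.4: "PFS is defined as the time from randomization until objective demonstration of tumor progression or death, whichever occurs first". PFS is also Secondary Endpoint #3.
- Immune response is an exploratory endpoint (sections 3.2.1 and 8.4.1). Protocol v7.0 section 3.1.3 expects it more often on DCVax-L.
- Protocol v7.0 Appendix A schedules immune draws at Time 0 (before injection), Day 20 and then to Month 30. Section 8.4 takes none after crossover.
- On pseudo-progression (PsPD) caused by the vaccine, SAP section 1.2.3 says: "This second form of PsPD occurs frequently in subjects receiving DCVax®-L, as may be seen through case studies". Section 8.3.2 expects early events to misstate true progression to different degrees in the two arms.

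No landmark time, estimand or caveat is attached to the three rows.

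**The concern.** A subgroup hazard ratio is a randomised comparison only if membership is fixed before treatment can act. Here it is not. For PFS, patients are sorted by the outcome being analysed. For OS, they are sorted by an event whose timing, or false detection, the product may change. For responders, they are sorted by a treatment effect that is measured only while the patient has not crossed over.

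The SAP argues repeatedly that progression events may obscure benefit. A hazard ratio in early progressors is a natural place to look for support for that argument, or against it. If the number mainly reflects who was sorted into the row, either reading is unsafe.

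**Working it through.** **1. Check of inputs.** The plan gives no figure for these subgroups, so its PFS sample size is reproduced first. Schoenfeld: d = (zα + zβ)² / [p₁p₂(ln HR)²], with HR = 7/11 = 0.636, one-sided α 0.01 (z = 2.326), power 84% (z = 0.994) and 2:1 allocation (p₁p₂ = 0.222). This gives 3.320² / (0.222 × 0.2043) = 243 events, against 248 stated (within 3%). Power at 248 events is 84.8%, against 84%.

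**2. PFS inside the PFS-defined groups.** Exponential rates are λ = ln2/7 = 0.0990 on placebo and ln2/11 = 0.0630 on DCVax-L. Among patients with PFS ≤ c, the hazard is h(t) = λe^(−λt) / (e^(−λt) − e^(−λc)).
- c = 2, t = 0: 0.0630/0.1184 = 0.532 against 0.0990/0.1797 = 0.551, ratio 0.966.
- c = 4, t = 0: 0.0630/0.2228 = 0.283 against 0.0990/0.3270 = 0.303, ratio 0.934.
- As t approaches c, both hazards behave as 1/(c − t), so the ratio tends to 1.

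The Cox HR averages between these limits. The large-sample score equation gives 0.98 and 0.96; simulations gave 0.98 to 1.00 and 0.95 to 0.97. A true 0.64 has almost vanished, because everyone in the group has an event by month c by construction.

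**3. Group sizes.** With 232 DCVax-L and 331 − 232 = 99 placebo patients, PFS ≤ 2 months holds about 232 × 0.118 = 27.5 against 99 × 0.180 = 17.8. PFS ≤ 4 months holds about 51.7 against 32.4. If all die, the 95% interval factors are exp(1.96√(1/27.5 + 1/17.8)) = 1.82 and exp(1.96√(1/51.7 + 1/32.4)) = 1.55.

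**4. OS with no true effect, false progression on DCVax-L.** Assumptions: time to progression has median 7 months, with a further 9 months' median to death, in both arms. A stated share has progression called falsely at a uniform time between 1 and 4 months. OS HR in all patients is 1.00.

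| False PD, DCVax-L / placebo | OS HR, PFS ≤ 4 months |
|---|---|
| 10% / 0% | 0.86 |
| 20% / 0% | about 0.78 |
| 30% / 0% | 0.72 |
| 30% / 20% | about 0.93 |
| 30% / 30% | about 1.00 |

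In PFS ≤ 2 months the first three rows give about 0.90, 0.82 and 0.78, but only because calls may fall before month 2. If false calls start at month 2, when the first on-study MRI is scheduled, the HR is about 1.00. The ≤ 4-month values barely change.

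**5. OS with no true effect, progression truly delayed.** Second model: PFS medians 7 and 11 months, Gaussian copula correlation with OS of 0.3 to 0.7 (assumed), censoring at 60 months. OS HR is 1.20 to 1.28 in PFS ≤ 2 months and 1.19 to 1.30 in PFS ≤ 4 months, a false harm. With the SAP's assumed OS effect (17/25.3 = 0.672) the ratios are 0.83 to 0.90 and 0.82 to 0.88, so the effect is diluted. With no effect on either endpoint (correlation 0.5), the subgroup ratios return to 0.99 to 1.01.

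**6. Responders, no true effect.** Same copula model, with assumed response per draw of 30% to 50% on DCVax-L and 5% to 15% on placebo, drawn only while progression-free. OS HR is 1.06 to 1.26 in responders and 1.12 to 1.84 in non-responders. If response on DCVax-L also tracks prognosis, responders give 0.85 to 0.97 and non-responders 1.79 to 2.13.

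**7. Complement.** In PFS > 4 months, OS HR is about 1.00 under step 4 and 1.04 to 1.09 under the OS null of step 5.

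**The case against.** Much of the case on the other side stands.

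- The rows carry no alpha and are outside the confirmatory subgroup hierarchy of section 8.1.1. Section 6 places formal claims on the ITT population.
- The groups are small, and the SAP addresses pseudo-progression separately through confirmed PFS and the analyses of ultimately unconfirmed progression.
- Table 5 is limited by data. Table 3 shows published subgroup curves only for MGMT, age and residual disease, and the external controls received no DCVax-L, so they supply no matching responder group.
- SAP v1.0 gives no timing for responder status. That it arises after dosing is inferred from its definition and the sampling schedule. The Day 20 draw precedes the first on-study MRI, so a responder need not have survived long.

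A reader might infer something stronger: that with no survival effect the plan would show DCVax-L prolonging life in early progressors and responders. The documents do not support that. The early-progressor result needs an excess of false progression on DCVax-L. Section 1.2.3 also attributes pseudo-progression to surgery and radiation, which both arms received, and its figure of up to 30% describes brain cancer patients generally. For responders, the simple null points towards false harm.

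What does not stand is exploratory status as a defence. It answers multiplicity; it does not make a biased ratio interpretable.

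**Conclusion.** The point holds as a risk of misinterpreting exploratory results. Followed as written, section 8.3.5 yields hazard ratios that are not treatment effects in these three rows.

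The loss of the PFS effect (0.64 becoming about 0.95 to 1.00 inside the two progressor Yes groups) needs only the SAP's medians and exponential times. The OS distortions need assumed rates and correlations that the documents do not give. They run from about 0.72 to about 1.30 in early progressors, with no bias in the step 4 model when false-progression rates are equal. The 2-month OS figures under false progression hold only if it is called before the month-2 scan. Responder ratios run from about 0.85 to 1.26. OS bias in the PFS > 4 months complement is small.

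No primary or formally tested secondary analysis is affected.

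**What to change.** Remove the rapid-progressor, early-progressor and immunological-responder rows from the treatment-HR subgroups in Tables 5 and 8. If the groups are of interest, report descriptive landmark summaries within each arm: classify patients still at risk at month 2, month 4 or one fixed immune draw by their status to date, and count survival from that landmark. Give no between-arm or external-control hazard ratio for these groups as a treatment effect.

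The change is to SAP wording only. The SAP describes itself as preceding data lock and unblinding, so it can be made without knowledge of results. The cost is three exploratory sets of hazard ratios.

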#### 8.3.2 Analysis for OS, PFS

The intent of the original protocol was that the Cox proportional hazards model will be used for the primary analysis of OS. However the OS endpoint analysis may be confounded by non-proportional hazards due to the effects of the crossover option that was built into the protocol from the outset. Under this crossover option, all subjects from both arms of the Trial were allowed to opt to receive the active treatment DCVax®-L at the time of disease progression (measured by MRI), while remaining blinded to their initial treatment assignment. If subjects originally assigned to placebo receive treatment benefit in terms of extended survival as a result of this crossover option, then we can expect the survival curves to converge. To address possible non-proportionality while controlling type I error, a testing procedure based on a weighted log-rank statistic that was developed by Karrison will be used [28].

The intent of the original protocol was that the Cox proportional hazards model will be used for the primary analysis of PFS. When the protocol was developed in 2006 the phenomenon of pseudo-progression was largely unknown. Since then, pseudo-progression has become well recognised as a

major issue. It is now expected that, because early events specifically may not represent true disease progression, differentially in the two randomized groups, the proportional hazards assumption may not hold; the hazard ratio is expected to decrease with time as the effect of PsPD decreases.

For OS and PFS, Karrison's approach to the weighted log rank test will be used [28], based on the ITT population. A one-sided p value will be presented.

Along with the p value for the test, the hazard ratio, with a 95% confidence interval, will be presented. Estimates of 6, 12, 18, 24, 30, 36, 42, 48, 54 and 60 month OS and PFS will be provided, with 95% confidence intervals, for both randomized treatment groups.

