#### 13.7. SECONDARY ANALYSIS OF COVARIATES

Associations of 1) age, 2) KPS, 3) extent of resection, 4) clinical site, and 5) Temodar® usage with the primary endpoint and first secondary endpoint will be assessed. Proportional hazards regression modeling will be done to determine the sets of covariates independently associated with the endpoints and also to evaluate interactions of these covariates with the effect of treatment with DCVax-Brain. All randomized patients will be included in the analysis.

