## **Protocol 020221 Summary of Changes**

Protocol version, date	Main Characteristics or Changes in Trial Design
v1.0 – v3.2	Open label study, under which only 3 subjects were enrolled. These 3 subjects are not part of the Phase III ITT population.
v4.0, 22 October 2007  Original Protocol of Randomized Controlled Trial	
 
Randomized, placebo-controlled design
 
Primary endpoint is PFS, OS is secondary endpoint
 
Crossover option for all subjects from both arms of the trial to receive DCVax®-L following tumor recurrence
 
Planned enrollment of 240 subjects, randomized 2:1
 

v5.2, 7 May 2012 	
 
Designated as Phase III (from Phase II)
 
Addition of several tertiary/exploratory endpoints
 

v6.0, 24 February, 2014 	
 
Addition of Absolute Lymphocyte Count as a covariate
 
Increase in sample size to 348 subjects
 

V6.1, 5 November 2014	Addition of additional evaluations (including IDH-1 mutational status)
v7.0, 23 September 2020 Final Protocol	
 
Several changes to conform to the Statistical Analysis Plan (SAP), dated 23 September 2020
 
Primary endpoint: OS for newly diagnosed glioblastoma patients, compared to external controls
 
Secondary endpoint: OS for recurrent glioblastoma patients, compared to external controls
 
SAP included as Appendix to the Protocol
 
The SAP v1.0 governs all analyses for the study
 

- The Original Protocol also included an "Informational Arm" for subjects who failed to meet the eligibility criteria for enrollment in the trial. These patients were treated in a separate cohort outside the trial on a compassionate use basis.
- In this Protocol, new enrollment in the Information Arm cohort was terminated.
  - Also in this Protocol, a new separate "Pseudo-Progression Arm" cohort was established for patients who failed to meet the eligibility criteria for the trial because of apparent pseudo-progression. These patients were treated outside the trial on a compassionate use basis.
-  This Protocol removed the Pseudo-Progression Arm.

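### SAP 8.3.5 reports within-trial OS and PFS effects in 60 separate subgroup levels but plans no comparison between levels, so the descriptive tables are easy to misread

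*Combined protocol and SAP*

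**What the plan says.** SAP Section 8.3.5 states: "The analyses described for the ITT population will all be repeated for each of the following subgroups". The list follows under "Table 8: Planned subgroup analyses", and the section closes with "The hazard ratio for the treatments, and a 95% confidence interval for the HR, will be estimated for each subgroup".

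The ITT analyses being repeated are those of Section 8.3.2 and the Cox models of 8.3.4. For the weighted log-rank test, 8.3.2 says "A one-sided p value will be presented" and then "Along with the p value for the test, the hazard ratio, with a 95% confidence interval, will be presented". Read literally, each subgroup level therefore receives a p value as well as a hazard ratio and interval, for OS and again for PFS. The closing sentence of 8.3.5 by itself asks only for estimation.

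On comparing levels, Sections 8.3.2 to 8.3.5 are silent. The covariate step in 8.3.4 item 1 screens main effects. The one sentence on interactions, "Interactions are tested using the same likelihood test", stands in 8.3.4 item 2, where the question is whether an effect changes over time segments. Protocol v4.0, Section 13.7, did plan "also to evaluate interactions of these covariates with the effect of treatment with DCVax-Brain". That version is superseded, and the Summary of Changes says "The SAP v1.0 governs all analyses for the study", so this is background and not a contradiction.

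**The concern.** A subgroup table raises one question: does the treatment effect differ between levels? A result inside one level does not answer it. Each level holds only part of the events, so power falls, and one level can reach significance while another misses it although the true effect is the same in both. A reader who sees an interval excluding 1 in one MGMT or PD-L1 level and including 1 in the other may conclude that the vaccine works only in the first.

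The documents give some reason to expect such reading. SAP Section 6 intends baseline and genetic factors to inform the interpretation of the endpoints, and Protocol v7.0 Section 9.3 mentions the search for prognostic or predictive markers. A predictive marker is, by definition, a treatment-by-marker interaction. Lymphocyte count and monocyte PD-L1 are each cut three ways, so each has three chances to produce the pattern.

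**Working it through.** **Count of Table 8.** MGMT 2; resection 2+2; age 5; sex 2; KPS 3; lymphocytes 2+2+2; RPA 2; race 2; residual size 4; tumor PD-L1 2; monocyte PD-L1 2+2+2; CD8 2; immunological responders 2; histology 4; Immunoscore 6; biomarkers 4; rapid progressors 2; early progressors 2. The sum is 60 levels in 23 splits, 17 of them two-level. Responders, rapid progressors and early progressors are defined after randomization. Without them, 60 − 6 = 54 levels and 23 − 3 = 20 splits remain.

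**Inputs (SAP 1.3).** PFS: medians 7 and 11 months, HR = 7/11 = 0.636, one-sided 0.01, 84% power, 248 events. OS: medians 17 and 25.3 months, HR = 17/25.3 = 0.672, one-sided 0.025, 80.5% power, 233 events. Allocation 2:1, so P₁P₂ = 2/9.

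**The plan's own figures.** Events = (z_α + z_β)² / [P₁P₂ (ln HR)²].
- PFS: (2.326 + 0.994)² / (0.2222 × 0.2043) = 243, against 248 stated.
- OS: (1.960 + 0.860)² / (0.2222 × 0.1581) = 227, against 233 stated.

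Both agree within 3%. The stated event counts are used below.

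**Power inside one half.** Significant here means that the 95% interval lies below 1. Power = Φ(√(d × 2/9) × |ln HR| − 1.96), with d the events in the level. The ordinary log-rank test stands in for the weighted test.
- PFS, d = 124: Φ(5.249 × 0.452 − 1.96) = Φ(0.413) = 66%.
- OS, d = 116.5: Φ(5.088 × 0.398 − 1.96) = Φ(0.063) = 53% (0.525).

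**Exactly one half significant under a uniform effect**, 2p(1 − p):
- PFS: 2 × 0.660 × 0.340 = 45%.
- OS: 2 × 0.525 × 0.475 = 50%.

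An interaction test at 5% errs in about 5% of cases under the same truth.

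**Variations.**
- A 30/70 split gives 53% (PFS) and 55% (OS).
- With 232:99 allocation (331 − 232 = 99), equal halves give 46% and 50%.
- If OS deaths reached 300, an assumed figure, equal halves give about 47%.

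**Whole table.** 1,500 trials were simulated at the planned size with a uniform effect, exponential times, equal-sized levels and factors unrelated to outcome.
- On average 34 (PFS) or 27 (OS) of 60 levels were significant.
- About 12 to 13 of 23 splits were mixed, and more than 99% of trials had at least one mixed split.
- Among the 17 two-level splits, 7.2 (PFS) or 8.2 (OS) were mixed, while the interaction test was significant in about 1.0.

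This run includes the three post-randomization splits as if they were baseline factors. A separate simulation of the 54 baseline levels, taken as 21 groupings with 232:99 allocation and OS HR 0.672, also gave at least one mixed grouping in over 99% of trials.

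**Power of the interaction test**, equal halves, true difference equal to the overall log HR. SE = √[2 / (d × 2/9)].
- PFS: SE = 0.269; Φ(0.452/0.269 − 1.96) = 39%.
- OS: SE = 0.278; Φ(0.398/0.278 − 1.96) = 30%.

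**The case against.** The strongest reply is that Table 8 is descriptive. It has no alpha and no decision rule. The gatekeeping in 8.3.1 covers only the ordered secondary endpoints, the subgroups that do carry alpha are the external-control ones in 8.1.1, and SAP Section 6 rests formal claims on the ITT population. This stands. A reader might infer that the plan inflates formal type I error or will claim benefit in Table 8 subgroups; the documents support neither.

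A reader might also infer that the plan leaves no means of judging heterogeneity. That is too strong. Where levels do not overlap, the reported hazard ratios and intervals allow the ratio and its standard error to be worked out. What is missing is a requirement to report it.

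The remedy has limits too:
- Interaction tests have low power here.
- Twenty baseline splits tested at 5% would give at least one false signal with probability up to 1 − 0.95²⁰ = 64% if independent.
- Section 8.3.2 expects that hazards may not be proportional for OS and PFS.
- One linear term per marker imposes a shape.

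These points call for a careful form of the fix. They do not favour level-by-level significance, which is wrong far more often when the effect is uniform.

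**Conclusion.** The point holds as a reporting gap in the within-trial subgroup analyses. No primary or gatekept secondary conclusion depends on it.

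A reader might infer that a uniform effect will look selective for any given characteristic. The figures do not say that: for one two-level split it is close to a coin flip (45 to 50% with equal halves, up to 55% at 30/70). Near certainty applies only to finding at least one mixed split somewhere in the table, and characteristics with four to six levels contribute strongly to that.

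The sizes rest on the planning hazard ratios, the planned event counts and assumed subgroup sizes. The documents give neither actual subgroup sizes nor final event counts. Protocol v7.0 Section 9.3 warns that genomic and immune assays depend on spare tissue, so some levels may be much smaller. The IDH1 and 1p19q entries have no listed complement and cannot show a one-level-against-the-other pattern. The post-randomization subgroups raise a separate question not argued here.

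**What to change.** Amend SAP 8.3.5 as follows:
- For each baseline characteristic, fit a model with treatment, the characteristic and their interaction. Report the ratio of hazard ratios with its 95% interval and one interaction p value.
- Show level-specific hazard ratios and intervals in a forest plot, without level-specific p values.
- Label Table 8 descriptive, with no multiplicity control.
- Treat the three cut-points for lymphocyte count as one characteristic, and likewise those for monocyte PD-L1, for example as one interaction on the measured scale with a check of linearity. This reduces 20 baseline splits to 16. The chance of at least one false interaction is still up to 1 − 0.95¹⁶ = 56% if independent, which is why the label is needed.
- State that the ratio of hazard ratios is an average effect if hazards are not proportional.
- State that a non-significant interaction is not evidence of a uniform effect.

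Extending the set to confirmed PFS is optional. The cost is SAP wording and modest programming, with no new data. The main downside is the low interaction power shown above, so a real difference can be missed; the level-specific estimates stay visible.
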